1.0 SUMMARY of INVESTIGATION

Study Title:	Prospective, Parallel, Multicenter Randomized Controlled Study Investigating the Effects of UVC Beam and Laser Beam Therapy According to Standard Therapy in Patients with Covid-19 Diagnosis
Study Code:	MD2020/001
Device :	Turkishbeam Model Number: 1007-001
	*: The device was produced by RD GLOBAL ARASTIRMA GELISTIRME SAĞLIK ILAÇ INSAAT YATIRIMLARI A.S.
Device Classification:	Class III
Purpose of the Study:	Clinical research study that evaluates the effect of Turkish Beam- Selective UV developed by RD GLOBAL ARASTIRMA GELISTIRME SAĞLIK ILAÇ INSAAT YATIRIMLARI A.S. use into Intravascular, Intrapulmonary, Intratracial, Intrarespiratory area. Bacteria, Fungal and Virus-based pathogens systematically to collect and evaluate specific clinical performance and safety data. In our Clinical Research, we aimed to investigate the effectiveness of the treatment group and control group mortality rates, intensive care hospitalization times, monitoring the virus load by PCR, and the treatment effectiveness of UVC

Scope of the Study:	This Clinical Research covers determining the treatment effectiveness and reliability of UVC application to patient groups, the details of which are determined in the protocol.
Application:	Intravascular, Intrapulmonary, Intratracial, Intrarespiratory UVC and Laser Therapy System
Overall Study Design:	Prospective, Parellel, Multicenter, Randomized Controlled
Number of volunteers:	50 patient- 2 groups with 25 (two hundred) patients in each group
Treatment Groups:	Test: Antiviral + Antimalarial + Antibiotic Treatment + UVC Therapy Control: Antiviral + Antimalarial + Antibiotic Treatment
Groups of Volunteer:	Those who are between the ages of 40-75 and who have applied to the clinic with symptoms such as fever, weakness, cough, and shortness of breath, or who have signs of COVID-19 (SARS- CoV-2) test positive or atypical pneumonia findings in CT findings and accepted as COVID 19 infection, and patients undergoing intubation treatment in intensive care unit
Sensitive population / Vulnerable subjects:	The study will not include under-40, pregnant women and those with suspected pregnancy, previously diagnosed with mental disorders, puerperant women and lactating women

Duration of the clinical trial: 3 months (04.2020- 07.2020)

Researched Medical Condition:

and Disease

According to ICD 10 coding; B34.9 Virus infection is not defined, B34.2 CORONA VIRUS INFECTION UNDEFINED B97.2 Colon virus, causative agent of diseases classified in other sections B97 Viral agents, the cause of diseases classified in other sections B99 infectious diseases, other and unspecified A49.9 bacterial infection not defined

Manufacturer of the Device:

RD Global Arastirma Gelistirme Sağlık Ilaç Insaat Yatirimlari A.S.

Ethics Committees:	Gaziantep University, Klinik Arastirmalar Etik Kurulu
IKU Statement:	This study will be conducted in accordance with the principles of Good Clinical Practice (IKU), the Declaration of Helsinki and the requirements of the legal documents published on this subject.
Privacy:	The name of the Clinical Research Coordinator, Responsible Researcher and Assistant Researcher will be included in the reports. The names of the patients will be kept Confidential. Patient datas will be used by assigning CODE to each patient. Data privacy will be ensured under the "KVKK" (PDPL-Personal Data Protection Law). Identification information / personal identifier of the volunteers such as Patient card, Patient diary will be collected or accessed.
	It will be ensured that the relevant person to be researched has a written consent based on adequate information about the nature and results of the research and that this consent is not dependent on any benefits. Responsible / assistant researchers will receive relevant written commitment on ethics, confidentiality and "PDPL" on this issue.

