5.5 Primary Endpoints

• Ending the vital functions of the patient (medically accepted ex)

Or

- Gloskow Coma Level 13 and above,
- At least 3 days body temperature must have remained normal (measurement from the ear 37.5 C)
- Respiratory symptoms should be significantly improved
- The nucleic acid test must be negative in 2 consecutive tests for the respiratory pathogen (sampling interval must be more than 24 hours)
- Obvious healing of lesions with CT
- There should be no comorbidity or complications requiring hospitalization
- Without oxygen support SaO2 should be> 93%

All of its items have been realized

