5.6 Secondary Endpoints

- Hypersensitivity
- Temporary shortness of breath
- Rarely, redness of the skin is due to heat
- Edema
- Bleeding
- Embolization
- Hematoma
- Hyperpigmentation
- Ache
- paresthesia
- Superficial thrombophlebitis
- May cause urticaria or ulcers.
- Vascular rupture and perforation
- Visible scratch
- Iatrogenic injury may damage the surrounding tissues.
- Hemothorax or pneumothorax.
- Neighboring Nerve Damage Iatrogenically
- phlebitis
- Skin Burn or discoloration

If two or more adverse effects from the above adverse effects are seen, the study is terminated.

6. Statistical Evaluation:

- According to the course of the clinical trial, if we reach the research arm (100 patients), control group (100 patients), the efficacy and safety of the treatment will be examined and an interim report will be prepared. According to the results of the interim report, the clinical trial will be terminated or the clinical trial will be continued until the number of volunteers (400 in total) mentioned above is completed.
- In this interim analysis, the patients completing the study will be evaluated considering the primary and secondary endpoints stated in the protocol and the criteria are as follows:

1-Duration in intensive care

2-Survival rate

Contribution of UVC and laser beam application to the treatment of 3-COVID 19 infection and / or superinfections accompanying COVID 19 infection

The tests to be applied are as follows:

1-Difference test between two averages for intensive care stay

(Mann-Whitney U test or t test) will be used.

2-Survival analysis tests will be used for survival rate.

Accompanying 3-COVID 19 infection treatment and / or COVID 19 infection

To investigate the contribution of UVC and laser beam application to the treatment of superinfections

Chi-square test will be applied.

Descriptive statistics will also be given for demographic data.

REFERENCE STUDIES ABOUT THE APPLICATION OF UVC BEAM "in vitro, in vivo and ex vivo"

1. The Effect of UV-C Ray Reducing Pathogen Rate on Blood Platelets Apps;

Auto-immune diseases HIV 1 -2
T-lymphotropic virus types 1 and 2
Hepatitis B (HBV)
Hepatitis C (HCV)
Hepatitis A and E
Blood pathogens (Treponema pallidum)
Parvovirus B19

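### The plan gives two sample sizes, 50 and 400, and its only interim analysis (100 per arm) cannot be reached if the trial has 50 patients

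*Combined protocol and SAP*

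**What the plan says.** The number-of-volunteers line in Section 1.0 reads "50 patient- 2 groups with 25 (two hundred) patients in each group". Its numerals and its words disagree.

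Section 6 (Statistical Evaluation) plans one interim: "if we reach the research arm (100 patients), control group (100 patients), the efficacy and safety of the treatment will be examined". The consequence is that "According to the results of the interim report, the clinical trial will be terminated or the clinical trial will be continued", and continuation means that recruitment is "continued until the number of volunteers (400 in total) mentioned above is completed". The only earlier statement of a number of volunteers is the Section 1.0 line.

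The evaluation criteria (intensive care stay, survival, contribution to treating the infection or superinfection) are introduced by "In this interim analysis, the patients completing the study will be evaluated considering the primary and secondary endpoints stated in the protocol". The methods follow under "The tests to be applied are as follows": Mann-Whitney or t test, survival analysis, and chi-square. That list is not tied to the interim or to any other time point. The document gives no significance level, power, effect size, event rate or dropout assumption.

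**The concern.** The recruitment target and the interim trigger cannot both be right if the Section 1.0 numerals govern. A site reading Section 1.0 would stop at 25 per arm. A statistician reading Section 6 would wait for 100 per arm before looking at the data, and might then expect a further 200 patients.

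The analysis depends on the same figure. The criteria are framed as those of the interim, so a trial that ends at 50 has no analysis expressly assigned to it. A trial of 400 has an interim that examines efficacy and may end the study, but the plan does not say whether that would be for benefit, futility or harm, or at what level. Precision on mortality, a stated aim in Section 1.0 and part of the primary endpoint in Section 5.5, also differs greatly between the two sizes.

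**Working it through.** **Counts in the plan.** Inputs are from Section 1.0 (50; 25; two hundred) and Section 6 (100 + 100; 400).

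- Numerals: 2 × 25 = 50, which matches the stated 50.
- Words: 2 × 200 = 400, which matches the 400 in Section 6.
- Ratio: 400 / 50 = 8.
- Interim: 100 + 100 = 200 patients. This is 200/400 = 50% of the larger trial, but 200/50 = 4 times the whole of the smaller one (100 per arm against a maximum of 25).

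Each version is coherent in itself, and the two are incompatible. The intended size cannot be recovered from a power calculation, because the plan supplies none of the inputs.

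**What the difference means for mortality.** This is illustration only. The documents give no rates or level, so I assume a two-sided 5% level, equal arms and control mortality of 30–60%.

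*Precision.* Half-width of the 95% interval = 1.96 × √(2p(1−p)/n), with the same true mortality p in both arms.

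| p | n = 25 per arm | n = 200 per arm |
|---|---|---|
| 0.30 | 25.4 points | 9.0 points |
| 0.40 | 27.2 | 9.6 |
| 0.50 | 27.7 | 9.8 |
| 0.60 | 27.2 | 9.6 |

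*Power for 50% v 30% mortality.* The log-rank test is closest to the planned survival analysis. With proportional hazards, HR = ln(0.7)/ln(0.5) = 0.515 and |ln HR| = 0.664. Expected deaths are n × (0.5 + 0.3), which gives 20 or 160. Power = Φ(|ln HR| × √(deaths/4) − 1.96).

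- 25 per arm: Φ(1.486 − 1.96) = 0.318
- 200 per arm: Φ(4.202 − 1.96) = 0.988

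Other tests of the two proportions:

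| Test | 25 per arm | 200 per arm |
|---|---|---|
| Pooled normal approximation | 0.299 | 0.985 |
| Uncorrected chi-square, full enumeration | 0.334 | 0.984 |
| Fisher exact, full enumeration | 0.232 | 0.980 |

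*Absolute reduction detectable with 80% power, control mortality 30–60%.*

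| Test | 25 per arm | 200 per arm |
|---|---|---|
| Fisher exact | about 30–41 points | about 12–14 points |
| Uncorrected chi-square | about 27–37 points | about 12–14 points |

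At 25 per arm and 30% control mortality, either test needs almost no deaths in the test arm.

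**Error rate if the total is 400.** Suppose p < 0.05 at either look counted as success. With looks at half and full information, the two statistics have correlation √0.5, and the chance that at least one exceeds 1.96 in absolute value under no effect is 0.083 for one criterion. Two-look O'Brien-Fleming limits of 2.797 and 1.977 (nominal p of 0.0052 and 0.048) bring it back to 0.05. A stop allowed only for futility or harm would not inflate it.

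**The case against.** The best reply is that this is an incomplete edit. The words in Section 1.0, the total of 400 and an interim at exactly half of 400 fit one design, and the numerals may be a later change that was not carried through. That is plausible, but the text does not say so, and both figures are current.

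The interim is also conditional on reaching 100 per arm. At 25 per arm the condition can never be met, so the conditional wording does not remove the conflict.

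A fair limit concerns the tests. Section 6 lists them without a time point, so they could be applied to whatever sample is obtained, and they would be the same at 50 or 400. What is missing is when they are run, whether an earlier look exists, and which run is final. The missing final analysis and stopping level would be gaps even if the size were clear. They are secondary to the contradiction.

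Section 1.0 also gives a three-month duration, and Section 5.6 has an adverse-effect termination rule. Either could end the study, but neither sets its size.

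Finally, the precision and power figures rest on assumed rates, and Fisher's test is not named in the plan. The choice of test moves the numbers by a few points (10 for power at 25 per arm) and leaves the contrast between the two sizes intact.

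**Conclusion.** The concern holds and must be fixed. The sample size is stated as both 50 and 400, and the interim at 200 patients is impossible under the first. This follows from the plan's own counts and needs no assumption.

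The practical consequences rest on the assumed 5% level and mortality rates. The smaller trial would leave the mortality difference uncertain by more than 25 points either way and have about 32% log-rank power for 50% v 30%. The larger would give about 9–10 points and about 99%. The 8.3% error rate applies only if the total is 400 and an unadjusted p < 0.05 at either look counted as success.

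**What to change.** State one total and one per-arm number, in matching numerals and words, in Sections 1.0 and 6, and say what the number is based on.

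- **If 50:** delete the interim at 100 per arm and the continuation to 400. State that the Section 6 criteria and tests are the final analysis. Report the precision that 25 per arm gives (about ±25 to 28 points on mortality under the assumptions above).
- **If 400:** correct Section 1.0, write the final analysis, and say whether the interim may stop the trial for efficacy. If it may, give it a group-sequential boundary, for example two-look O'Brien-Fleming with nominal p of about 0.005 and 0.048. Check that the three-month duration still fits.

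Section 6 lists three unranked criteria, and a boundary protects only one. If a single confirmatory criterion is chosen, reconcile it with the Section 5.5 primary endpoint (death, or all recovery items met).

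The cost is mainly wording in two sections, with no patients added to whichever total is true. If 400 governs and efficacy stopping is allowed, the final nominal level falls from 0.05 to about 0.048.

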2.0 DESIGN of STUDY

2.1 DESIGN

Prospective, parallel, multicentre, randomized controlled study Ages between 40 and 75 years of age and positive symptoms such as fever, malaise, cough, and shortness of breath, or positive atypical pneumonia in CT findings or COVID-19 (SARS-CoV-2) test In the intensive care unit, which is accepted as COVID 19 infection and has been treated, patients will be treated with UVC radiation and laser beam treatment according to IKU principles in addition to Antimalarial therapy + Antiviral therapy + Antibiotic therapy. Standard

treatment consisting of Antimalarial therapy + Antiviral therapy + Antibiotic therapy will be applied to the control group. The dosage of the standard treatment consisting of antimalarial therapy + Antiviral therapy + Anitibiotic therapy, the number of days of treatment, and its active ingredient are indicated in the table.

Treatment in Possible / Definitive COVID 19 Cases with Pneumonia						
Oseltamivir** tb 75 mg	2x75 mg, oral	5 days 5 days				
Hydroxychloroquine, 200 mg tablet	Following 2x400 mg loading dose, 2x200 mg tablet orally	5 days				
According to the physician's d	ecision					
+\$	Day 1 500 mg, oral	5 days				
Azithromycin ***	4 days following 250 mg/day					
Severe cases that did not respo	ond to the first treatment					
Favipravir 200 mg tablet	2 x 1600 mg 2 x 600 mg	5-7 days				
Or						
Lopinavir 200 mg / ritonavir 50mg tablet	2 x 2 tablet, oral	10-14 days				

Source: COVID-19 (SARS-CoV2 INFECTION) GUIDE (Scientific Board Study) T. C. MINISTRY OF HEALTH 25 MARCH 2020

3.0 AIM of THE STUDY

With the application of ultraviolet light, it is aimed to treat the patient by seriously reducing / eliminating the burden of microorganism and inflammation in the patient body. The proposed treatment is an antimicrobial treatment strategy, and it is recommended to combine the supportive treatments with this process in terms of a holistic treatment strategy according to the clinical course of the disease.

4.0 INFORMATION ABOUT STUDY

Mechanism of Action

Ultraviolet (UV) irradiation is electromagnetic irradiation with a wavelength (100-400 nm) shorter than visible light (400-700 nm) but longer than x-rays (<100 nm). UV irradiation is divided into four separate spectral areas, including vacuum UV (100-200 nm), UVC (200-280 nm), UVB (280-315 nm) and UVA (315-400 nm). The mechanism of UVC inactivation of microorganisms is to damage the genetic material in the nucleus of the cell or nucleic acids in the virus. The UVC spectrum, especially the 250-270 nm range, is strongly absorbed by the nucleic acids of a microorganism and is therefore the inactivation wavelength range for microorganisms. This range, with a peak antimicrobial wavelength of

254nm, is known as the antimicrobial spectrum. Light-induced damage to the DNA or RNA of a microorganism usually results from dimerization of pyrimidine molecules. In particular, thymine (found only in DNA) produces cyclobutane dimers. When thymine molecules are dimerized, it becomes very difficult for nucleic acids to multiply, and if replication occurs, it often produces damage that prevents the viability of the microorganism. [1].

4.1 Usage Areas of UV

- Air Sterilization
- Surface Sterilization
- Water Sterilization, Water Treatment systems
- Instrument and Equipment Disinfection
- Disinfection of Food Packaging
- Use of tuberculosis patients in the ventilation system.
- It has many applications including the use of UVC in odor control, wastewater facilities, farms, commercial kitchens (HVAC) and food processing facilities.
- UVC germicidal lamps are also critical for purifying the air in industries where harmful and toxic chemicals such as printing, plastic and rubber are produced.
- In the disinfection of the air and surfaces of the operating rooms, Clean Room laboratories and biological safety cabinets, and inhibition of microorganisms in the air in the production area with UV-C light applications.
- Blood products have the potential to significantly reduce hepatitis C virus (HCV) infections.
- It is frequently used in sterilization of blood and plasma products.

4.2 Properties of UV

- 4.2.1 UV Properties UV 254 nm UV-C ray:
 - It is a well-known and essential antimicrobial agent.
 - Produces non-lethal pathogen damage to stop proliferation and increases sensitivity to immune system disruption.

450 nm Blue Laser beam:

- It regulates our biological rhythms.
- It regulates hormone balance.
- My vitamins increase absorption.
- It regulates the release of serotonin and cortisol.

535 nm Green Laser beam:

- To improve the behavior and functions of red blood cells,
- Increases the flexibility of red blood cells and provides more oxygen to the tissues.
- Improves hemodynamics with decreased blood viscosity.
- It has the feature of enabling restorative and balancing ways.

630 nm Red Laser beam:

- Increases cellular energy level.
- It reduces the production of proinflammatory cytokines.
- Immune regulates cell functions, slows or stops infection.

The effects of LED phototherapy depend on wavelength, power density, bacterial amount (or number), and species. Growth of S. aureus, E. coli and P. gingivalis increased at 625 nm, while 425 and 525nm showed bactericidal effect. In particular, S. aureus is inactivated only by applying 525 nm. [9].

The bactericidal effects of 625, 525 and 425 nm wavelength LED irradiation were investigated in vitro for anaerobic bacteria Porphyromonas gingivalis and two aerobes (Staphylococcus aureus and Escherichia coli DH5a). [9]. It shows that 625nm irradiation has potential applications for oral periodontal disease. This can be expected to have additional benefits for tooth whitening and resin curing in dental clinical practice. Irradiation at 625 nm can reduce inflammatory reactions and induce cell proliferation in periodontal disease involving the interaction of bacteria and oral cells. However, we can conclude that 625 nm irradiation has potential applications for periodontal. [9].

Blue light with wavelengths ranging from 400 to 470 nm has been reported to be effective for inhibiting various bacteria and fungi. Both experimental data and model simulation results have shown that 415-nm light has a more effective antifungal result that deals less damage to epithelial cells than 405-nm and 450-nm light. [3].

[figure not shown]
4.3 Precautions

[figure not shown]
- In the use of the product only, it should be performed by physicians who are cardiovascular surgeons, chest diseases, thoracic surgeries, intensive care specialists who will intervene with the patient with the tractors who have been trained in the product. In addition, the relevant branches (cardiovascular surgery, thoracic diseases, thoracic surgery, intensive care specialist) who will use the product in the clinical field, responsible researchers and assistant researchers will be planned and delivered about the device.
- Inspect product packaging prior to use.
- Do not use if sterile barrier is opened or damaged.
- Use prior to expiration date.
- Before starting the procedure, using protective glasses with UV filter feature for the patient, using eye bands for the patient to completely close the eyes when they do not have glasses.
- Use of UV filter protective glasses for the physician or healthcare personnel to use the device.
- Before using this product, principles, clinical practices, and associated risks must be fully learned.
- Each set used in treatment is for single use. It should not be used in the treatment of patients other than infection risk. SHOULD NOT BE STERILIZED AGAIN.
- If need to use The Disposable Steerable Catheter (disposable CAMERA CATHETER) and the fiberoptic line should be checked for operation before use; make sure that the size and shape of the catheter is suitable for the procedure to be performed
- Do not resterilize, as device performance may be compromised and there is an increased risk of cross contamination due to improper rework.

- If you encounter difficulties during the process, identify the cause of the strain before continuing
- Do not expose the product to autoclave or organic solvents.
- Pay attention to the expiration date stated on the package.
- Do not use the product that has exceeded the origin.
- Check the package and the material before use.
- Do not use the product that shows any problem.
- Use an appropriately sized guiding catheter or a guiding sheath.
- If you have difficulty during the procedure, identify the cause of the strain before continuing.

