4.7 Selective Permeable Effective Ultraviolet Wavelength Determination to be Applied

The ultraviolet C (UVC) beam is an alternative methods to existing methods used in the treatment of localized infections. Some drug resistant microorganisms have also been found to be sensitive to UVC irradiation. UV radiation can kill all kinds of microorganisms with its short wavelength and high energy. The greatest antimicrobial activity is in the wavelength region of 250-264 nm.

Contrary to what is known, UVC, selected with appropriate doses, can selectively inactivate microorganisms while maintaining the viability of mammalian cells and has also been proven to promote wound healing. UVC (200nm - 280 nm) has been proven to cause less damage to tissue than UVB in animal studies. [one]. Although UVC can cause DNA damage in mammalian cells, it can be quickly repaired by DNA repair enzymes. [one]. In summary, UVC is an innovative treatment method of our age as an alternative approach to existing methods used for localized infections, single stranded RNA and double stranded DNA viruses, especially for the treatments caused by highly antibiotic-resistant microorganisms. UVC should be used in such a way that side effects are minimized and the resistance of microorganisms to UVC is prevented.

4.8 Benefits / Risks:

Risks from implementation:

-Vascular rupture

- -If the guide cannula moves out of the target, tissue damage and radiation-related damage
- -Depending on the place of application, thrombosis

-Pulmonary tissue damage

- -Pnomotoraks
- -Hemotoraks

Risks from the beam device: Retinal damage and vision loss

The risks mentioned above are due to the fact that the work team is selected from experienced and competent people.

has been minimized. They will also undergo a separate training for applications. Already intensive care and intubation in intratracheal / pulmonary / intravascular interventions In addition to the risks that may occur under the

It stands out.

On the other hand, it is compulsory to use ultraviolet-proof glasses as specified in the protocol for the patient who performs the application. There is no additional risk that may arise from the device.

However, the benefit that will arise from beam application is very high compared to these risks.

With the treatment we envisaged, survival will increase significantly.

We think that the duration will be shortened and superinfections will be prevented. Summarized benefit / risk

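### The eyewear rule in section 4.3 requires UV filtering only, although the research arm also receives laser and every laser the protocol lists is visible light

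*Combined protocol and SAP*

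**What the plan says.** Section 4.3 sets the eye protection. For the patient it asks for "using protective glasses with UV filter feature for the patient", with a fallback: "using eye bands for the patient to completely close the eyes when they do not have glasses". For staff it asks for "Use of UV filter protective glasses for the physician or healthcare personnel to use the device" and offers no alternative.

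Section 4.8 (Benefits / Risks) lists "Risks from the beam device: Retinal damage and vision loss". It then states that "it is compulsory to use ultraviolet-proof glasses as specified in the protocol for the patient who performs the application", and the next sentence reads "There is no additional risk that may arise from the device".

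The intervention is wider than UV. Section 1.0 gives the application as a combined UVC and laser system. Section 2.1 adds laser to UVC for the treated patients, section 5.4.1 assigns both to the research arm, and section 6 plans to evaluate the contribution of both. Section 4.2 lists three lasers, beginning with "450 nm Blue Laser beam" and followed by green at 535 nm and red at 630 nm, alongside the 254 nm UVC source. Section 4.0 defines ultraviolet as "electromagnetic irradiation with a wavelength (100-400 nm) shorter than visible light (400-700 nm").

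**The concern.** The protocol describes two kinds of light and names an eye injury as the hazard of the beam device, but its written eyewear standard addresses only one of them. A lens chosen to filter ultraviolet need not attenuate blue, green or red laser light, and nothing in the readable text asks that it should.

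Those affected are research-arm patients who are given glasses and the staff who treat them. The patients are intubated in intensive care and may be unable to report a visual symptom. The adverse effects listed in 5.6 include no eye event, and the visit schedule names no eye examination, only general physical examination and adverse-event recording. Prevention through the eyewear rule is therefore the main eye safeguard in the text.

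**Working it through.** The plan states no figure to reproduce here. The check compares the listed wavelengths with the protocol's own bands, and then compares each eye measure with the light it is required to stop.

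**Step 1: wavelengths (4.2) against bands (4.0: UV 100-400 nm, visible 400-700 nm).**

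| Source | Wavelength | Minus the 400 nm UV limit | Band |
|---|---|---|---|
| UVC | 254 nm | 254 − 400 = −146 nm | UV |
| Blue laser | 450 nm | 450 − 400 = +50 nm | visible |
| Green laser | 535 nm | 535 − 400 = +135 nm | visible |
| Red laser | 630 nm | 630 − 400 = +230 nm | visible |

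All three lasers lie in the visible band (each is also below 700 nm). None lies in the UV band.

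**Step 2: who must be protected against what, in the readable text.**

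| Person | Measure | Required against UV | Required against 450, 535, 630 nm |
|---|---|---|---|
| Patient with glasses | UV-filter glasses (4.3) | yes | no |
| Patient without glasses | eye band closing the eyes (4.3) | yes, by inference | yes, by inference |
| Operator and other staff | UV-filter glasses (4.3) | yes | no |

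That the eye band works at any wavelength is inferred from its closing the eyes completely; the protocol does not say so. Section 4.8 adds no separate specification, because it points back to what the protocol already specifies. Whether its sentence concerns the patient or the operator is unclear, but the glasses are ultraviolet-proof either way. The glasses, goggles and face protection in 4.6 are infection-control equipment with no optical requirement.

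**Step 3: is laser part of the treatment?** Sections 1.0, 2.1, 5.4.1 and 6 say that it is. Against this, the test-group line in 1.0 mentions only UVC, and the three written procedures in 5.4.1 (intravascular, intratracheal, orotracheal or nasotracheal) are all titled UVC; 0 of 3 contain a laser step. Section 5.4.1 does not say which laser wavelengths are delivered.

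**Step 4: size of the hazard.** Estimating eye exposure would need laser power, laser class, exposure time and lens transmission. The documents give none of these, so no estimate is possible.

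**The case against.** The strongest case on the other side is that no laser eye hazard has been shown. The laser wavelengths come from a background list of claimed biological effects, and no procedure contains a laser step. The intravascular steps place the fibre tip in the vessel before light is applied, and the intratracheal route runs through the endotracheal tube. Use is restricted to trained specialists, EN ISO 14971 on risk management is among the listed documents, and detailed lens ratings could sit in device instructions that we cannot see. A UV-filter requirement also sets a minimum and does not exclude broader lenses.

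Much of this stands as a limit on what can be concluded. A reader might infer that patients or staff will be exposed to harmful laser light in the open. The documents do not support that. The pre-use check of the fibreoptic line in 4.3 and the open-system procedure in 5.4.1 leave exposure possible, but they do not establish it or its size. A reader might also infer that the protocol contains no laser eye protection at all. That cannot be said, because a figure at the head of 4.3 is not shown and could carry a warning.

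None of this changes the written rule. Training and a risk-management standard do not tell a site which lens to use, and lenses that happen to block visible light are not the same as a requirement that they do. If laser is not in fact delivered, sections 1.0, 2.1, 5.4.1 and 6 need correcting instead.

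**Conclusion.** The concern holds as a gap in the specification. In the readable text, the eyewear rule in 4.3, repeated by reference in 4.8, covers UV only. Three of three listed lasers fall outside the UV band, and the only measure likely to stop them is reserved for patients without glasses. Full compliance would leave staff, and patients given glasses, with no required protection at any listed laser wavelength.

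This rests on two assumptions: that laser is delivered in the research arm, as four sections indicate, and that the lasers used are among those in 4.2. The mismatch in the text is clear. The clinical size of the hazard is unknown, and no confidence should be claimed about it.

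It is tempting to read 4.8 as claiming that ultraviolet-proof glasses remove all device risk. The two sentences are adjacent, but the surrounding text is broken, and the second may mean only that there is no risk beyond those already listed. The point does not depend on that reading.

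**What to change.** - In 4.3, and so by reference in 4.8, require eyewear rated for every wavelength actually delivered: 254 nm plus any of 450, 535 and 630 nm that are used. Apply this to the operator and the assistant.
- For every patient, require the same eyewear or the eye band that 4.3 already provides, whether or not the patient has glasses.
- In 5.4.1, state which laser wavelengths are delivered. If none is, correct the sections that say otherwise.
- Optionally, reword the sentence in 4.8 about no further device risk so that it cannot be read as following from UV-only glasses.

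The cost is a different eyewear specification, minor procurement and a few sentences of text. Sample size, visits and analysis are unaffected.
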